### Secondary objectives:

4. To provide VE estimates at day 90/180/365 (pending data distribution) after immunisation with a bivalent booster among immunocompromised individuals.

- 5. To provide VE estimates at day 365 after immunisation with a bivalent booster among females and males, and 50-69-year-olds and 70+-year-olds.
- 6. To provide VE estimates at day 365 after immunisation with a bivalent booster according to time since a previous infection.
- 7. To provide VE estimates at day 365 after immunisation with a bivalent booster according to time between-dose intervals (for both the primary course and the booster doses).
- 8. To provide VE estimates at day 365 after immunisation with a bivalent booster according to the vaccine brand received as fourth dose.

**Study design**: Nationwide register-based cohort analyses in Denmark, Finland, Norway, and Sweden during the study period from 27 December 2020 until latest available date in 2023 at time of analyses (e.g., 30 September 2023).

Population: Source cohorts will consist of all individuals who are known residents in the four Nordic countries and have received at least three vaccine doses (i.e., a primary two-dose vaccination course and one booster) with the AZD1222 (Vaxzevria, Oxford-AstraZeneca; as part of the primary vaccination only), BNT162b2, and/or mRNA-1273 vaccines between 27 December 2020 and latest available date in 2023. The main study cohort will consist of individuals who are at least 50 years of age in Denmark, 60 in Finland, 65 in Norway, and 50 in Sweden and eligible fourth dose recipients will include those receiving a fourth dose after (including on this day) 1 September 2022 in Denmark, 18 July 2022 in Finland, and 1 July 2022 in Norway and Sweden. Secondary study cohorts will consist of 1) main study cohort individuals hospitalized for Covid-19 and 2) immunocompromised individuals aged ≥18 years.

**Variables**: The outcomes of interest will be Covid-19 hospitalisation, Covid-19 mortality and all-cause mortality for the third primary objective. Covariates will be variables of demography, comorbidity, and previous Covid-19 infection and vaccination.

**Data sources**: Nationwide demography- and healthcare registers within each participating country.

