#### 9.3 Variables

#### **Exposures**

The Nordic countries implemented national vaccination campaigns against SARS-CoV-2 from December 27, 2020, providing free vaccinations to all residents. Phased distribution plans were implemented prioritising vaccination of individuals at highest risk of Covid-19 complications (nursing home residents, healthcare workers, and individuals of older age). Denmark and Norway almost exclusively used mRNA vaccines after full or partial discontinuation of AZD1222 in March 2021 due to serious but rare events of thrombosis with thrombocytopenia. The AZD1222 was similarly halted in Finland and Sweden for the younger population but continued as part of the utilized primary course schedules for the population older than 64 years. The mRNA vaccines have been predominantly used in all countries for booster vaccinations. Ad26.COV2.S has seen very limited use. The Nordic countries have vaccinated around 6 times more individuals with BNT162b2 than with mRNA-1273. Prioritized fourth dose vaccination rollouts to the vulnerable elderly and those living in nursing home

facilitieswere initiated in spring 2022 in Finland, Norway and Sweden, and has been offered more broadly to the general population since summer 2022. Fourth dose vaccination in Denmark was initiated in September 2022, coinciding with the time of the authorization of use of the bivalent boosters. Similar to previously received vaccination doses, the fourth vaccine dose has been classified according to vaccine brand and also according to whether it was a bivalent BA.1, bivalent BA.4-5, or monovalent (original) mRNA-booster vaccine.

For objective #3, we will for the 4 vs 3 dose comparison combine BA.1 and BA.4-5 bivalent boosters to increase statistical power. Depending on data availability, we will stratify this analysis by bivalent booster type.

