#### **Covariates**

For our main cohort analysis objective #1-2 and #5-8, we will take the following potential confounders into account: age (using birth cohort), sex, region of residency, calendar time of last mutual vaccine dose (i.e., either third or fourth dose depending on boosted vs unboosted- [i.e., 4 vs 3-] or between boosters- [i.e., 4 vs 4-] analyses), vaccination priority group (nursing home residents, healthcare personnel, at risk of severe Covid-19 due to comorbidities), previous SARS-CoV-2 infection and selected comorbidities. For the Covid-19 hospitalised cohort analysis (objective #3), we will also include length of hospitalisation as a covariate (as a proxy for severity of event) but not use previous SARS-CoV-2 infection history (as per eligibility criteria, all included are SARS-CoV-2 infected [as hospitalised due to this infection] and any previous SARS-CoV-2 infection is most likely not a strong confounder within the comparison). For the immunocompromised cohort analysis (objective #4), we will also include subtype of immunocompromised condition (as categorized in the 6 levels in the table above). In addition, we will assess the data distribution to help find the optimal categorization of the variables "Time since SARS-CoV-2 infection", "Time between primary course and first booster", and "Time between first and second booster". Further details of covariate definitions are provided in table below.

Variable	Country	Data source and details	Values/codes
Ago	Denmark	The Civil Registration System. Recorded birth year. Age defined as the country-specific start date minus birth year.	Categorical (for adjustment, using birth year): 5-year bins
Age	Finland	The Finnish Population Information System. Recorded birth year. Age defined as the country-specific start date minus birth year.	Binary (for stratification): ≥ 70 years</td

Variable	Country	Data source and details	Values/codes	
	Norway	Norwegian Population Register. Recorded birth year. Age defined as the country-specific start date minus birth year.		
Sweden		The Total Population Register. Recorded birth year. Age defined as the country-specific start date minus birth year.		
	Denmark	The Civil Registration System. Defined as registered sex.		
Sex	Finland	The Finnish Population Information System. Defined as registered sex.	Binary: male, female	
Jex	Norway	Norwegian Population Register. Defined as registered sex.	billary. maie, lemaie	

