## 9.7 Data analysis

#### **Procedures**

[figure not shown]
We will use a matched study design to evaluate the effectiveness of a bivalent BA.1 or BA.4-5 (or monovalent [original]) mRNA-booster vaccine (as the fourth dose) in comparison with having received three monovalent vaccine doses only (i.e., nonboosted with a fourth dose) as well as between fourth dose recipients. For the boosted vs nonboosted (i.e., 4 vs 3 dose) comparisons, individuals who have received a fourth dose will be matched on the day of vaccination with individuals who have not yet received a fourth dose. Individuals will be matched on age (5-year bins), calendar time according to when the third dose was received (monthly bins), and a propensity score including sex, region of residence, vaccination priority groups (i.e., individuals at high-risk of severe Covid-19 or healthcare workers), selected comorbidities (chronic pulmonary disease, cardiovascular conditions or diabetes, autoimmunity-related conditions, cancer, and moderate to severe renal disease), and previous history of SARS-CoV-2 infection characteristics. The day the fourth dose was administered within each matched pair will serve as the index date for both individuals. If individuals who were included as a

matched nonboosted (previously three-dose vaccinated) individual (i.e., a reference individual) received a fourth dose later than the assigned index date, they will be allowed to potentially re-enter as a fourth-dose recipient in a new matched pair on that given date. The figure below illustrates the study cohort construction.

For the between booster (i.e., 4 vs 4 dose) comparison, BA.4-5 booster and BA.1 booster recipients (as a fourth dose) will be matched on age (5-year bins), calendar time according to when the fourth dose was received (monthly bins), and a propensity score including sex, region of residence, vaccination priority groups (i.e., individuals at high-risk of severe Covid-19 or healthcare workers), selected comorbidities (chronic pulmonary disease, cardiovascular conditions or diabetes, autoimmunity-related conditions, cancer, and moderate to severe renal disease), and previous history of SARS-CoV-2

infection. The day the fourth dose was administered will serve as the index date for each respective individual. The figure below illustrates the study cohort construction.

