## Statistical analysis

We will use logistic regression to estimate the propensity score of receiving a specific booster dose given covariates as predictors. We will match (without replacements) on age, calendar time of last mutual vaccine dose (i.e., third or fourth dose), and the propensity score (with a calliper width of 0.01).

Cumulative incidences will be estimated by the Kaplan-Meier estimator, and from these we will calculate the comparative VE as 1 – risk ratio at day 365. The corresponding 95% CI will be calculated using the delta method. Country-specific estimates will be combined by random-effects meta-analyses implemented using the *mixmeta* package in R.

Comparative waning will be estimated using meta-regression.(39) First, we will estimate the VEs (in the specific comparison being evaluated) in each consecutive three-months period (day 8-90, day 91-180, 181-270, and 271-365) by stratification on time since booster vaccination. Second, the resulting estimates will be analysed using meta-regression to provide a ratio of VEs per three-month intervals as a measure of waning.

Subgroup analyses will be conducted according to sex, age groups ( $</\ge70$  years), time since last SARS-CoV-2 infection (<6, 6-12, >12 months), time between primary course and first booster ( $</\ge12$  months), time between first and second booster ( $</\ge12$  months), and bivalent booster brand (Pfizer-BioNTech and Moderna).

*All-cause mortality (objective #3)* 

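### No vaccine product is used for matching or adjustment, which leaves possible confounding by earlier-dose products, a BA.4-5 vs BA.1 result not attributable to strain alone, and 4 vs 4 brand strata without a stated within-brand match

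*Protocol*

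**What the plan says.** Section 9.7 (Procedures) lists both matching sets item by item.

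- **Boosted vs nonboosted (4 vs 3):** "Individuals will be matched on age (5-year bins), calendar time according to when the third dose was received (monthly bins), and a propensity score including". The variables named for the score are sex, region, priority group, comorbidities and infection history.
- **Between boosters (4 vs 4):** "matched on age (5-year bins), calendar time according to when the fourth dose was received (monthly bins), and a propensity score including sex", followed by the same kinds of covariate.

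The confounder list in Section 9.3 (Covariates) agrees. It opens with "age (using birth cohort), sex, region of residency, calendar time of last mutual vaccine dose" and continues with priority group, previous infection and comorbidities. The intervals between doses appear in the covariate table for stratification only. The objective 3 Cox model in Section 9.7 takes the main-analysis covariates, drops previous infection and adds length of stay. None of these lists contains a vaccine product.

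The data exist. Section 9.3 (Exposures) states, by analogy with earlier doses, that "the fourth vaccine dose has been classified according to vaccine brand and also according to whether it was a bivalent BA.1", BA.4-5 or monovalent product. On overall use it says: "The Nordic countries have vaccinated around 6 times more individuals with BNT162b2 than with mRNA-1273".

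Brand is used only for stratification. The subgroups in Section 9.7 end with "and bivalent booster brand (Pfizer-BioNTech and Moderna"), and the example table in Section 12 repeats the strata under BA.4-5 vs BA.1. How pairs are handled within those strata is not stated.

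**The concern.** The emulation table in Section 9.1 assumes randomization conditional on the matched baseline covariates, so whatever is left off the list is assumed not to matter. Three things are at stake.

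1. **Earlier products.** AZD1222 vs an mRNA-only primary course, and the brand of the third dose, could be related both to fourth-dose uptake or type and to residual protection at the index date. In 4 vs 4 the only vaccination variable matched is the month of the fourth dose, which is the exposure's own date. Third-dose month is not matched there.
2. **Composition and brand.** Section 1 lists BA.1 and BA.4-5 versions of both Comirnaty and Spikevax, and Section 9.1 defines the strategies by bivalent type alone. A pair may therefore set one manufacturer's BA.4-5 product against the other's BA.1 product.
3. **Brand strata in 4 vs 4.** If the strata are cut from the pooled matched cohort, cross-brand pairs lose a member and the balance that matching provided is no longer assured. If instead one member's brand defines the stratum, the comparison is not within brand.

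**Working it through.** **Inputs from the protocol.** Overall BNT162b2 to mRNA-1273 ratio about 6:1 (Section 9.3), so the mRNA-1273 share is 1/7 = 14.3%. Expected numbers are 1.6 million BA.4-5, 1.0 million BA.1 and 0.9 million monovalent (Section 9.5). These sum to 3.5 million against the stated 3.4 million, within the rounding range of 3.35 to 3.65 million. Previous VE is 67.8% (BA.4-5) and 65.8% (BA.1) (Section 7). The protocol does not give brand shares by bivalent type.

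**Assumptions.** r is the mRNA-1273 to BNT162b2 risk ratio; pA and pB are the mRNA-1273 shares in the BA.4-5 and BA.1 arms.

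**Step 1: brand-induced risk ratio when BA.4-5 and BA.1 do not differ.** RR = [1 + pA(r − 1)] / [1 + pB(r − 1)].

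| pA | pB | r | RR |
|---|---|---|---|
| 1/7 | 1/7 | any | 1.00 |
| any | any | 1 | 1.00 |
| 0.10 | 0.25 | 0.90 | 0.990/0.975 = 1.015 |
| 0.10 | 0.25 | 0.85 | 0.985/0.9625 = 1.023 |
| 0.10 | 0.40 | 0.90 | 0.990/0.960 = 1.031 |
| 0.10 | 0.40 | 0.85 | 0.985/0.940 = 1.048 |

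Reversing the imbalance reverses the direction: pA = 0.25, pB = 0.05, r = 0.80 gives 0.96. A more extreme case, pA = 0.05, pB = 0.50, r = 0.80, gives 1.10.

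**Step 2: plausibility of the shares.** Weighting by 1.6 and 1.0 million, 10%/25% implies (0.16 + 0.25)/2.6 = 15.8% mRNA-1273 overall, and 10%/40% implies (0.16 + 0.40)/2.6 = 21.5%. The protocol's 14.3% is closer to the milder case. The check is rough, because that ratio is not specific to bivalent fourth doses.

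**Step 3: scale.** The previous VEs imply an indirect BA.4-5 vs BA.1 risk ratio of 0.322/0.342 = 0.94. This is a ratio of two separate comparisons and serves only as a yardstick.

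**Step 4: pair breaking.** If pairs form independently of brand, the cross-brand share is pA(1 − pB) + pB(1 − pA). With 1/7 in both arms:

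- cross-brand: 12/49 = 24.5%
- both BNT162b2: 36/49 = 73.5%
- both mRNA-1273: 1/49 = 2.0%

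Of the 7/49 of pairs whose BA.4-5 member had mRNA-1273, only 1/49 has a same-brand partner. Six of seven mRNA-1273 recipients would lose their match. No brand effect needs to be assumed for this step.

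**Step 5: earlier products in 4 vs 3.** Assume an AZD1222 primary course in 20% of boosted and 40% of nonboosted people, with a risk ratio of 1.2. The spurious RR is (0.8 + 0.2×1.2)/(0.6 + 0.4×1.2) = 1.04/1.08 = 0.963. Removing it moves VE from 65.8% to 1 − 0.342/0.963 = 64.5%, and from 67.8% to 1 − 0.322/0.963 = 66.6%. The assumed imbalance would have to remain after matching.

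**The case against.** A fair defence has several parts.

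- **Fourth-dose brand is a version of the treatment, not a baseline confounder.** Section 9.9 says the analyses reflect vaccination strategies as initiated at the time, and objective 1b does not claim attribution to strain. This stands: the all-brand estimate is a legitimate target.
- **The conditions for distortion are not shown.** Section 7 cites a US cohort with similar effectiveness of the two bivalent brands, and Section 9.9 says booster type was assigned unselectively to the authors' knowledge, apart from two early weeks in Denmark. This also stands, although neither statement gives the brand mix by bivalent type.
- **AZD1222 is partly handled.** Denmark and Norway used almost only mRNA vaccines after March 2021. In Finland and Sweden AZD1222 use followed age, which is matched, and analyses run within country. Third-dose month is matched in 4 vs 3. This removes part of the link in 4 vs 3 and less in 4 vs 4.
- **Re-matching within strata may be left to the analysis scripts.** That is possible, so the strata are at risk rather than shown to be invalid.
- **Product covariates may cost pairs.** Under a 0.01 calliper this is true and belongs in the cost.

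The abstract's promise, "Covariates will be variables of demography, comorbidity, and previous Covid-19 infection and vaccination", might be read as contradicted by the later lists. It is not, because dose month is a vaccination covariate in a general sense.

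**Conclusion.** The omission is real and worth correcting; its effect is possible, not demonstrated.

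A reader might infer that BA.4-5 vs BA.1 is in fact a Moderna vs Pfizer contrast, or that earlier products confound every comparison. The protocol supports neither. The first needs both unequal brand shares and a brand effect. The second needs an association that survives matching on age and dose month within country.

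What holds is narrower:

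- Residual confounding by earlier products is possible, most plausibly in 4 vs 4. In 4 vs 3 it would be about one percentage point of VE even under the assumed AZD1222 imbalance.
- The all-brand BA.4-5 vs BA.1 result compares boosters as rolled out. Attributing it to strain carries a possible distortion of about RR 1.02 to 1.05 under the assumed 10% vs 25–40% shares and brand risk ratio of 0.85–0.90. It is exactly zero if either condition fails.
- The BA.4-5 vs BA.1 brand strata would break about a quarter of pairs if cut from the pooled cohort, assuming the 6:1 ratio in both arms and pairing independent of brand. In 4 vs 3 the boosted member's brand sets the stratum and pairs stay intact, so that part of objective 8 is unaffected.

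**What to change.** (a) Add primary-course type (any AZD1222 vs mRNA only) and third-dose brand to the propensity scores in all matched comparisons and to the objective 3 Cox model. Both are baseline variables already in the registers.

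(b) Add a BA.4-5 vs BA.1 analysis matched exactly on fourth-dose brand and take the 4 vs 4 brand strata from it. Keep the all-brand estimate as the main result, described as the effect of composition together with brand mix. Reporting brand by bivalent type in each country would show whether the distinction matters.

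The cost is one extra matched run per country and some lost pairs, both under the 0.01 calliper in (a) and in the brand-exact run, mainly where one brand was rarely used for one bivalent type. The number lost cannot be computed from the protocol, because brand by bivalent type is not given.

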Treatment strategies	
 
Have an immunocompromised condition         (ascertained by registered diagnosis of solid         malignancy, hematologic malignancy,         rheumatologic or inflammatory disorder, other         intrinsic immune condition or immunodeficiency,         organ or stem cell transplant, or received a Covid-         19 vaccine dose equivalent of booster dose for         immunocompromised)
 
For the target trial comparing booster vs unboosted:         1) Receive a BA.1 or BA.4-5 bivalent booster         2) Do not BA.1 or BA.4-5 bivalent booster and         continue being unboosed during follow-up
 
For the target trial comparing between boosters:         1) Receive a BA.1 bivalent booster         2) Receive a BA.4-5 bivalent booster         3) Receive an original monovalent         The bivalent (or original monovalent) booster is         received as a 4th dose within the general population         (objective #1-#2, #5-#8) and as any booster (≥4th)
 
	Same as for the target trials. We define the date of booster vaccination (that is, the index date) according to the registered date of administration.
	dose for the immunocompromised population	
	(objective #4)	
Treatment assignment	Individuals are randomly assigned to a strategy at baseline in a 1:1 ratio (for immunocompromised population, conditional on number of previous doses received). Individuals will be aware of the assigned treatment strategy.	Individuals are assigned to the strategy compatible with their type of booster received; randomization is assumed conditional on matching (in a 1:1 ratio) on baseline covariates; unboosted are assigned the index data of the matched booster.
		date of the matched booster recipient.
Outcomes	Covid-19 hospitalization (ascertained by positive SARS-CoV-2 PCR test in relation to Covid-19 registered inpatient hospitalization) and Covid-19 death (ascertained by positive SARS-CoV-2 PCR test in relation to any (or Covid-19 cause-specific [in Norway]) death.	Same as for the target trials.
Follow-up	Follow-up for each individual will start at day 8 from	Same as for the target trials.
	treatment assignment (to ensure full immunisation among booster recipients) and end on day of outcome event, death, loss to follow-up, receipt of additional booster, 365 days (and 180 days for immunocompromised population) after baseline, or end of data collection, whichever occurs first.	
Causal contrast	Per-protocol	Observational analog to per-

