We will follow individuals from day 8 after the index date (to ensure full immunisation among booster recipients) up until the day of an outcome event, 365 days has passed since the index date (i.e., allowing up to 357 days of follow-up since day 8), receipt of additional booster, death, emigration, or end of the study period, whichever occurs first.

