These abovementioned potential limitations are mitigated by our utilization of an active comparative design as opposed to comparisons with unvaccinated. In the 4 vs 3 comparisons (i.e., fourth dose boosted vs nonboosted), the follow-up among those who have not received a fourth dose is contributed from individuals who have yet to receive a fourth dose and individuals who will never receive a fourth dose. In the more immediate time-periods following the index date, the comparison is dominated by the former group while closer to day 365 of follow-up the comparison is dominated by the latter group. Individuals who never receive a fourth dose are more likely to be different from those who elect to get booster vaccination and this can introduce e.g., healthy vaccinee bias if these differences are not accounted for by the included covariates.

Our statistical precision will rely on the overlap of covariate distributions between comparisons (affecting the final matched cohort sizes). As a consequence, the possibilities for direct head-to-head comparison between bivalent and monovalent boosters as a fourth dose will most likely be limited due to the less overlap of calendar periods of use and the need for stringent control hereof (due to otherwise potential confounding by e.g., differences in waning of third dose, background population infection rates, and circulating variants).

Both vaccination status and SARS-CoV-2 variants of predominance are strongly correlated with calendar time. This limits possibilities for directly comparing effectiveness estimates obtained during different variants predominance periods (background transmission rates and population characteristics most likely differ) as well as evaluating longer-term follow-up effectiveness in relation to only one SARS-CoV-2 variant. As such, the analyses will instead reflect evaluations of the initiated Covid-19 vaccination strategies at that given time.

We aim to perform a panel of different subgroup and secondary analyses to extend current knowledge of the impact of timing of vaccination in relation to both previous SARS-CoV-2 infection and vaccination schedules received. However, we do not aim to address hybrid immunity of vaccination followed by a subsequent infection on future Covid-19 risk, given that such analysis with use of observational data would be hampered by collider bias.(40)

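### In the 4 vs 3 dose comparisons, unweighted censoring at the fourth dose lets the reference arm drift towards never-takers, so day-365 VE and the waning ratio can be biased in either direction

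*Protocol*

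**What the plan says.** The target-trial table in Protocol section 9.1 sets a per-protocol contrast. The unboosted strategy is to "continue being unboosed during follow-up", and "randomization is assumed conditional on matching (in a 1:1 ratio) on baseline covariates".

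Under Procedures in section 9.7, follow-up runs from day 8 to day 365 unless ended sooner by an outcome event, "receipt of additional booster, death, emigration, or end of the study period, whichever occurs first". An unboosted person who later takes the dose leaves the reference arm, and "they will be allowed to potentially re-enter as a fourth-dose recipient in a new matched pair on that given date".

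Under Statistical analysis, "Cumulative incidences will be estimated by the Kaplan-Meier estimator". The effect measure is "comparative VE as 1 – risk ratio at day 365", and "The corresponding 95% CI will be calculated using the delta method". The same approach is applied in four consecutive quarters, and those estimates feed the meta-regression for waning.

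Section 9.9 describes the reference arm as a mixture of people not yet boosted and people who will never be boosted. The first group prevails early, but "closer to day 365 of follow-up the comparison is dominated by the latter group". It adds that never-takers are likely to differ and that healthy vaccinee bias can follow if the covariates do not capture the difference.

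Section 9.8 offers a later start of follow-up (day 21/28) and a shorter horizon if the data cannot support day 365.

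**The concern.** A per-protocol curve for staying unboosted is valid under Kaplan-Meier only if, given what the analysis adjusts for, people who take the fourth dose and leave have the same later risk as those who remain. Matching secures comparability at the index date. It does not secure it among those still under observation months later. If uptake during follow-up depends on age, comorbidity or region, even the matched covariates can drift apart. Infection history is also fixed before the fourth-dose rollout (section 9.3 covariate table), so an infection after index that alters both uptake and risk is never taken into account.

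Two primary objectives are exposed. Day-365 VE weights the late quarters fully, and the waning measure is the trend across quarters, which is where the mix changes. Waning and a changing reference group would look alike. The planned confidence interval reflects sampling error only and would not reveal the problem.

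**Working it through.** **The plan's own figure.** Follow-up from day 8 to day 365 is 365 − 8 = 357 days, as section 9.7 states. The protocol gives no never-taker share, uptake speed or risk contrast, so everything below is an illustration on assumed inputs.

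**Assumed inputs**
- Never-takers are 30% of both arms at index. The arms are thus balanced, as section 9.1 assumes.
- The other 70% would take the fourth dose after a mean of 40 days (constant rate 1/40 per day).
- Takers have an outcome hazard of 0.00002 per day without the dose. Never-takers have k times that.
- True VE by quarter is 65, 40, 20 and 0%.
- Unboosted people are censored when they take the dose, without weights. Boosted people stay in follow-up.

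**True day-365 VE.** Counting both end days, the quarters have 83, 90, 90 and 95 days. The average risk ratio is (83 × 0.35 + 90 × 0.60 + 90 × 0.80 + 95 × 1.00) / 358 = 0.698, so VE is 30%.

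**Drift of the reference arm.** The never-taker share among those still unboosted at day t is n(t) = 0.3 / (0.3 + 0.7·exp(−t/40)). It is 34% at day 8, 80% at day 90, 97.5% at day 180 and above 99% from day 270. The average over days 8–365 is 0.88.

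**What the plan would return.** For small risks, estimated VE = 1 − RR × (0.7 + 0.3k) / (1 + (k − 1)·n̄), where n̄ is the average never-taker share in the period. At day 365:
- k = 1.25: 1 − 0.698 × 1.075 / 1.220 = 0.385
- k = 1.5: 1 − 0.698 × 1.150 / 1.440 = 0.443
- k = 0.8: 1 − 0.698 × 0.940 / 0.824 = 0.204

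Summing the daily hazards without the small-risk approximation gives:

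| Never-taker risk ratio k | Day 8–90 | 91–180 | 181–270 | 271–365 | Day-365 VE |
|---|---|---|---|---|---|
| 1 (no bias, equals truth) | 65.0% | 40.0% | 20.0% | 0.0% | 30% |
| 1.25 | 67.2% | 47.5% | 31.0% | 14.0% | 38% |
| 1.5 | 68.8% | 52.6% | 38.4% | 23.3% | 44% |
| 0.8 | 62.7% | 31.0% | 6.2% | −17.5% | 20% |

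**Effect on waning.** From first to last quarter the true risk ratio rises 1.00/0.35 = 2.86-fold. The plan would show 0.860/0.328 = 2.62-fold at k = 1.25, 0.767/0.312 = 2.46-fold at k = 1.5 and 1.175/0.373 = 3.15-fold at k = 0.8. Higher-risk never-takers hide part of the waning, and lower-risk never-takers exaggerate it.

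**Death, taken separately.** Assume a one-year outcome risk of 1% unboosted, a hazard ratio of 0.5, and yearly mortality of 6% unboosted and 3% boosted. The Kaplan-Meier VE is 1 − 0.005013/0.010000 = 49.9%. The Aalen-Johansen risk is λ/(λ + μ) × (1 − exp(−(λ + μ))), with λ the outcome hazard and μ the death hazard. It is 0.004937 boosted and 0.009697 unboosted, so VE is 49.1%. The difference is about one point.

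**The case against.** The strongest reply is that the protocol already discloses this drift, that matching is rich (age, third-dose month, priority group, five comorbidities, previous infection and more), and that bias arises only if never-takers still differ in risk after it. At k = 1 there is none. That stands, and it is why neither size nor direction can be claimed. But disclosure is not an analysis, and neither item in section 9.8 targets the drift: the day 21/28 start deals with effects close to vaccination, and the shorter horizon applies only when data are too thin. Nor is this a detail left for a statistical analysis plan, because the protocol itself fixes the censoring rule and the estimator.

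A reader might infer four stronger claims that the documents do not support.
- *That all primary comparisons are affected.* In the 4 vs 4 comparisons both arms have had the fourth dose and the censoring event is a further one, so the never-taker mechanism does not apply.
- *That the partner always stays in follow-up.* Section 9.7 speaks of following individuals and does not state a partner rule, while section 9.8 mentions heavy censoring of pairs. If pairs are censored together, balance on the matching variables is better preserved and mainly unmeasured selection remains.
- *That the bias is larger, for example 43, 51 or 15% in place of 38, 44 or 20%.* Those values arise if the boosted arm contains takers only while 30% of the unboosted arm are never-takers from the index date. That adds baseline confounding, which censoring weights would not remove.
- *That censoring at death requires a new primary estimator.* Death does not cause the drift, and its effect on VE is small at the mortality assumed above.

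**Conclusion.** The point holds for objectives 1a and 2a. The protocol combines a per-protocol contrast, baseline-only matching, censoring at the fourth dose and an unweighted Kaplan-Meier estimator. It then states that the late reference arm is dominated by people who probably differ, and plans nothing to measure the consequence. Confidence in the mechanism is high. Size and direction are open. Under the stated assumptions a true day-365 VE of 30% would be reported as anything from about 20% to 44% for k between 0.8 and 1.5, with the waning trend distorted to match. The partner rule is unclear between sections 9.7 and 9.8. Death as a competing event is a separate, minor matter.

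**What to change.** For the 4 vs 3 comparisons:

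- Add inverse-probability-of-censoring-weighted estimates of day-365 VE and of the quarterly VEs. Weight for uptake of the fourth dose in the unboosted arm and of the next dose in the boosted arm, using the matching covariates, calendar time and infection since index. Report them beside the unweighted estimates, with numbers at risk by quarter and arm.
- State in section 9.7 whether the partner is censored when one member of a pair is boosted, bring section 9.8 into line, and run the other rule as a sensitivity analysis.
- Add an Aalen-Johansen analysis with death as a competing event as a sensitivity analysis, leaving the primary estimator in place.

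The cost is extra code in the R scripts shared by the four countries and wider late intervals. Weights remove only the part of the selection explained by measured variables, so the caveat in section 9.9 should stay.
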